4.7.2. Neurotoxicity Monitoring

Neurotoxicity, including changes in mental status, has been reported with other T-cell directed therapies including chimeric-antigen receptor (CAR)-T cells and CD3xCD19 based bispecific antibodies such as blinatumomab and rarely with flotetuzumab. The exact mechanism of the toxicity is unknown. As a result, additional monitoring of patients receiving flotetuzumab is indicated. An alteration in mental status refers to general changes in brain function, such as confusion, amnesia, loss of alertness, disorientation, defects in judgment or thought, and disruption in perception and psychomotor skills. Patients should be monitored for changes in mental status or other potential neurotoxic events and should be evaluated for orientation to time, place and person at baseline prior to treatment with flotetuzumab and at regular intervals during therapy. Any suspected neurotoxic event should prompt full evaluation including imaging studies, lumbar puncture and neurological consultation as indicated to rule out other causes. The incidence of CNS involvement by AML is low and routine lumbar puncture is not generally considered indicated. Patients with known, active CNS leukemia are excluded from the study and those with suspected disease must be evaluated by lumbar puncture prior to enrollment.

Patients need to be counseled during the consent process that they should NOT drive or operate heavy machinery while they are receiving flotetuzumab treatment and for 30 days after their last dose of flotetuzumab.

4.7.3. Tumor Lysis Syndrome

Prophylaxis for TLS should be administered for patients with active AML. Aggressive hydration, allopurinol, and oral phosphate binders should be implemented starting preferably 24 hours before flotetuzumab administration. Serum chemistries should be closely monitored during flotetuzumab administration in accordance with institutional standards for the treatment of acute leukemia. If TLS is observed, rasburicase should be considered for management as per

institutional standards. Patients who develop TLS should be monitored closely for abnormal serum chemistries or signs of end organ damage and treated appropriately.

4.7.4. Other Clinically Relevant Adverse Events

If a grade 3 non-hematological adverse event occurs that is deemed by the investigator to be possibly, probably or definitely related to the study drug, then flotetuzumab will be withheld until the toxicity resolves to no more than grade 1 (mild) after which flotetuzumab may be restarted at the previously tolerated dose. If the toxicity persists for more than 14 days, then flotetuzumab will be permanently discontinued. If a grade 4 non-hematological adverse event occurs that is deemed by the investigator to be possibly, probably or definitely related to the study drug, then flotetuzumab should be permanently discontinued.

4.7.5. GVHD

If a patient develops definitive evidence of acute GVHD⁶⁶, flotetuzumab will be permanently discontinued. Study therapy will be permanently discontinued should a patient develop definitive evidence of chronic GVHD.⁶⁷ See appendix for specific GVHD assessment criteria.

4.7.6. Immune-related Adverse Experiences

Immune checkpoint blockade has been associated with several syndromes associated with the breaking of immunological tolerance (19). Although not observed in non-clinical studies to date, similar events might occur in patients treated with flotetuzumab. These syndromes include pneumonitis, colitis, autoimmune hepatitis, arthritis, glomerulonephritis, myocarditis and cardiomyopathy, hypophysitis, thyroiditis, or other autoimmune endocrinopathies. The occurrence of any of these syndromes is an AESI. Their occurrence dictates interruption, and potentially discontinuation, of study drug administration pending further evaluation. In the event of suspected immune-related adverse experiences, the investigator should promptly consult with the Sponsor and early consideration should be given to the prompt implementation of systemic immune suppression utilizing agents that may include, but are not limited to steroids, anti-TNF α antibodies, and/or IL-6 receptor inhibitors.

4.7.7. Capillary Leak Syndrome

Risk of CLS has been associated with T-cell redirecting therapy, including chimeric antigen receptor (CAR)-T cell and CD3-engaging bispecific antibody-based molecules, and reported for the CD123-directed cytotoxin, tagraxofusp-erzs (Elzonris®). While CLS has not been observed

with frequency in patients treated with flotetuzumab, a detailed review of recent clinical data across all flotetuzumab studies identified 3 patients who received flotetuzumab monotherapy that, concomitant with CRS during multi-step lead-in dosing, exhibited rapid weight gain, decreased albumin, and systemic edema suggestive of CLS. Please be aware that CLS may or may not be associated with hemoconcentration in this patient population.

Healthcare professionals should monitor for weight gain of greater than 2.0 kg compared to the previous day's weight, fluid status, new onset or worsening edema, and decreased albumin. Patient's fluid status should be managed as clinically indicated with IV fluids and vasopressors if hypotensive, and with diuretics if normotensive or hypertensive until the patient's body weight normalizes. Flotetuzumab dose interruption should be considered. Further recommendations include administration of 10 mg dexamethasone or equivalent for patients with weight gain of greater than 2.0 kg, fluid overload, and edema, non-responsive to diuretics and/or fluid management.

4.7.8. Epstein-Barr Virus Reactivation

EBV belongs to the herpes virus family. After primary EBV infection, the virus quickly enters the latent phase and is characterized by a lifelong presence in B-cells. EBV-reactivation may occur in immune-compromised patients, and patients may experience signs or symptoms of mononucleosis, such as fatigue, weakness, fever, sore throat, and swollen lymph nodes. In immunosuppressed patients, including those who have received flotetuzumab, viral reactivation, specifically, EBV reactivation, has been reported. To date, on the CP-MGD006-01 study, four patients have experienced EBV reactivation. Reported symptoms included non-CRS related fever and fatigue. Rituximab (anti-CD20 antibody) is an effective treatment option in patients with EBV-reactivation and should be considered per institutional guidelines.

4.8. Permitted Medications and Supportive Therapies

All concomitant medications for medical conditions other than AML are permitted, as clinically indicated. All supportive therapies, other than anticancer treatment needed for the management of subjects enrolled in this study, are permitted including transfusional support as per institutional standards.

The following medications and supportive therapies are examples of supportive therapies that may be used during the study:

- Antibacterial, antifungal, or antiviral agents as prophylaxis and to treat active infections
- Antiemetics, antidiarrheals, anticholinergics, antispasmodics, antipyretics, antihistamines, analgesics, histamine receptor (H2) antagonists or proton pump inhibitors, and other medications intended to treat symptoms or signs of disease.
- Transfusions such as red blood cells and platelets are permitted to treat symptoms or signs of anemia or thrombocytopenia and should be documented on the concomitant medication form.

4.9. Prohibited Therapies

The following medications are prohibited during this study:

- Concurrent systemic corticosteroids at doses >10 mg of prednisone daily (or equivalent) except for mandatory premedication
- Any investigational agent
- Any vaccination except annual inactivated influenza and SARS-CoV-2 vaccination

4.10. Concurrent Antineoplastic Therapies

Cytoreduction with hydroxyurea will be allowed for the purposes of achieving an initial peripheral blast count $\leq 20,000/\text{mm}^3$ but must stop at least 24 hours prior to the protocol therapy. However, hydroxyurea may be reinstated at the discretion of the Investigator for the prevention or treatment of signs or symptoms of leukostasis during the time of study participation. The use of the following antineoplastic therapies will be specifically disallowed across all groups:

- Other cytotoxic chemotherapy
- Donor Lymphocyte Infusion
- Other monoclonal antibodies, antibody-drug conjugates, or bispecific T cell engager antibody constructs

The institution of any of the above should occur in the context of disease relapse or treatment failure leading to the discontinuation of the study treatment.

4.11. Duration of Therapy

Treatment is planned for up to five induction cycles and two cycles of consolidation. Treatment will continue until one of the following occurs:

1. Disease relapse after achieving a response

2. Serious illness that prevents further administration of treatment (i.e. progressive infection not responding to appropriate antibacterial and/or anti-fungal therapies)
3. Unacceptable adverse event(s)
4. Elective withdrawal of consent by the patient
5. Determination by the physician that it is no longer in the patient's best interest to continue the trial
6. Inability to tolerate the study drug
7. Initiation of breast feeding by the patient
8. Patient pregnancy
9. Delay of the study drug for more than 14 consecutive days due to unresolved toxicities
10. Completion of two consolidation cycles OR five induction cycles
11. No evidence of anti-leukemic activity (PR or better) after 2 successive cycles
12. Evidence of progressive disease

4.12. Duration of Follow-up

Patients will be followed for relapse and death for two years from the first day of the first cycle of treatment. Patients are routinely followed and monitored by JH physicians after alloHSCT or chemotherapy, and patients who complete the study and continue to receive their care at JH will have survival captured annually.

5. Disease Evaluations

5.1. Disease Status Definitions

Assessment of disease status will be performed based on the following definitions that have been modified from Dohner et al:⁶⁸

Complete Remission (CR)

- 1 Absence of extramedullary disease
- 2 Bone marrow blasts <5% blasts and absence of blasts with Auer Rods
- 3 Absolute neutrophil count (ANC) >1,000/ μ L
- 4 Platelets >100,000/ μ L
- 5 Red cell transfusion independence

CR with incomplete blood count recovery (CRi)

- Meets all criteria for CR except platelets and/or ANC

CR with partial hematologic recovery (CRh)

- Meets all criteria for CR except platelets ($\leq 100,000/\mu\text{L}$ BUT $> 50,000/\mu\text{L}$) AND/OR ANC ($\leq 1,000/\mu\text{L}$ BUT $> 500/\mu\text{L}$)

Partial Remission (PR)

- ANC $> 1,000/\mu\text{L}$ AND platelets $> 100,000/\mu\text{L}$ with a decrease of bone marrow blasts to 5-25% with at least a 50% reduction in bone marrow blasts from pretreatment levels

Morphologic leukemia-free state (MLFS)

- Bone marrow blasts $< 5\%$; absence of Auer rods; absence of extramedullary disease; no hematologic recovery required

Refractory Disease

- Failure to achieve CR after 1-2 cycles of treatment

Progressive Disease (PD)

- Increase of at least 25% in the absolute number of circulating or bone marrow blasts or development of extramedullary disease

Relapsed Disease

- Reappearance of blasts in the blood or bone marrow ($\geq 5\%$) or in any extramedullary site after a CR

Minimal Residual Disease (MRD)

- MRD in AML refers to the presence of leukemic cells below the threshold of detection by conventional morphologic methods. Patients who achieved a CR by morphologic assessment alone can potentially harbor a large number of leukemic cells in the bone marrow. This will be assessed using conventional MFC, wherein any measurable level of leukemic cells will be considered positive.³⁰ The MFC assay for LSCs developed by Gerber et al, NGS assay developed by

Onecha et al, and the 5-gene RQ-PCR assay developed by Goswami et al will also be used as exploratory correlative studies.⁵⁴

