8.1.2. Secondary Endpoints

8.1.2.1. Response-related Endpoints

- 1) Report the complete response (CR + CRi) rate in relapsed AML to flotetuzumab following alloHSCT.

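### No response definition in 5.1 requires blood free of blasts, so a patient with circulating leukemia can count as CR or CRi, and the same assessment can also be progressive disease

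*Combined protocol and SAP*

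**What the plan says.** Section 5.1 (Disease Status Definitions) gives five items for CR. Two concern disease: "Absence of extramedullary disease" and "Bone marrow blasts <5% blasts and absence of blasts with Auer Rods". The other three are an ANC threshold, a platelet threshold and independence from red cell transfusion.

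The related categories are built on the same list:

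- CRi: "Meets all criteria for CR except platelets and/or ANC".
- CRh: the CR items with relaxed count thresholds.
- MLFS: marrow blasts under 5%, with "absence of Auer rods; absence of extramedullary disease; no hematologic recovery required".

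Two other definitions in 5.1 do mention blood. Progressive disease (PD) is "Increase of at least 25% in the absolute number of circulating or bone marrow blasts or development of extramedullary disease". Relapse begins "Reappearance of blasts in the blood or bone marrow" and then names extramedullary sites as a further alternative.

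The secondary endpoint in 8.1.2.1 is "Report the complete response (CR + CRi) rate in relapsed AML to flotetuzumab following alloHSCT". Section 8.3.1 reports the CR rate with exact 90% binomial intervals, and Table 7 illustrates them for N=10 at one dose level.

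**The concern.** The plan treats circulating blasts as leukemia when it defines progression and relapse, but not when it defines response. A marrow count alone can therefore place a patient in the trial's only response endpoint while the blood differential still shows leukemia. Because PD can be met on circulating blasts alone, one assessment can satisfy both a response category and PD, and 5.1 sets no order of precedence. Two assessors following the text could record that assessment differently. At N=10, one such difference is visible in the reported rate.

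**Working it through.** **1. Does any response item cover blood blasts?** The CR items are extramedullary disease, marrow blasts with Auer rods, ANC, platelets and red cell transfusion. None refers to circulating blasts. CRi and CRh inherit the list with counts waived or relaxed. MLFS repeats the marrow and extramedullary items.

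**2. Could the extramedullary item cover it?** No. PD lists circulating blasts, marrow blasts and extramedullary disease as separate alternatives. Relapse likewise lists blood, marrow and extramedullary sites separately. Within 5.1, blood is not an extramedullary site.

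**3. Does another section catch it?** No. Inclusion criterion 10 (3.1) allows up to 20,000 peripheral blasts/mm³ at the start of Cycle 1. Section 4.4 applies the same ceiling to later cycles, consolidation included. Neither requires blood clear of blasts.

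**4. Illustrative records under the written text.** These are constructed, not trial data. In both, the patient has no Auer rods, no extramedullary disease, no red cell transfusion, ANC above 1,000/µL and platelets of 40,000/µL.

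| | Marrow blasts, baseline → Day 28 | Blood blasts/µL, baseline → Day 28 | Change in blood blasts | Category as written |
|---|---|---|---|---|
| A | 12% → 4% | 2,000 → 1,500 | (1,500 − 2,000)/2,000 = −25% | CRi |
| B | 8% → 4% | 2,000 → 2,600 | (2,600 − 2,000)/2,000 = +30% | CRi and PD |

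Both also meet MLFS. Record B takes the rise from baseline, because 5.1 does not state the reference point. Record A needs no such assumption.

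The overlap with PD is not confined to CRi. Take marrow blasts falling from 30% to 3% while blood blasts rise from 1,000 to 1,500/µL (+50%), with the other items met:

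- ANC 1,500 and platelets 150,000: CR and MLFS, and also PD.
- ANC 800 and platelets 80,000: CRi, CRh and MLFS, and also PD.
- ANC 300 and platelets 20,000: CRi and MLFS, and also PD.

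**5. Size at N=10 (the Table 7 denominator).** One patient is 1/10 = 10 percentage points. Table 7 prints 6-54 for a 30% rate and 15-65 for 40%. Those figures are reproduced by the normal approximation p ± 1.645√(p(1−p)/10):

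- 30%: 30 ± 23.8 = 6.2-53.8.
- 40%: 40 ± 25.5 = 14.5-65.5.

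They are not the exact intervals that the table title announces. That is a separate matter, but it explains why the figures below differ from the table. The exact (Clopper-Pearson) 90% limits are the 5% quantile of Beta(x, 11 − x) and the 95% quantile of Beta(x + 1, 10 − x):

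| Responders | Rate | Exact 90% CI |
|---|---|---|
| 2/10 | 20% | 3.7-50.7% |
| 3/10 | 30% | 8.7-60.7% |
| 4/10 | 40% | 15.0-69.6% |

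A true 3/10 with one miscounted patient is reported as 4/10. If all 16 patients allowed by 8.3.1 were pooled, one patient would be 1/16 = 6.25 points.

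**The case against.** The strongest reply is that the intent is clear. Relapse is worded as a reappearance in the blood, which presupposes that blood was clear at CR. The MRD entry in 5.1 places residual disease after CR below what morphology can detect. MLFS is, by name, a leukemia-free state. An experienced investigator would probably not call a patient with 1,500 blasts/µL a complete remission. This stands as evidence of intent, but it supplies no criterion. An unwritten rule may be applied unevenly, and the endpoint follows the written definition.

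The second reply is that little rests on the rate. It is a descriptive secondary endpoint in a trial whose primary aim is the MTD. No test, futility rule or expansion decision in 8.2 uses it, and the intervals for 3/10 and 4/10 overlap heavily. The blood differential would also be on record. All of this stands, and it limits how serious the point is.

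A reader might go further in three ways that the documents do not support:

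- **That blasts reappearing after an earlier CR create the same conflict.** Relapse is defined as following a CR, so the two states are sequential. The patient already counted as a responder, and the rate does not change.
- **That the plan gives opposing mandatory treatment instructions.** Section 4.2 makes responders eligible for consolidation, which is permissive, while 4.11 item 12 ends treatment on progression. The two can be read together as stopping. What remains is a double classification and treatment passages that need aligning.
- **That the reported rate will be inflated.** The documents do not say how often marrow blasts under 5% coexist with circulating blasts. To inflate the rate, such a patient must also meet the transfusion and extramedullary items and have no valid CR or CRi at another assessment.

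**Conclusion.** The definition is wrong as written. CR and CRi, the two categories in the response endpoint, can be met with leukemia in the blood. On a 25% rise in circulating blasts, the same assessment also meets PD with no precedence rule. The effect is 10 percentage points per miscounted patient at N=10, for example 3/10 (8.7-60.7%) becoming 4/10 (15.0-69.6%). No expected number of such patients can be derived.

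The core finding rests only on the text of 5.1 and 8.1.2.1. The overlap with PD also depends on the point from which the 25% rise is measured. The MTD decision is unaffected. The point should be corrected because it concerns the only response rate the trial reports and the data needed are already collected.

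**What to change.** For the CR + CRi endpoint (5.1, applied in 8.1.2.1 and 8.3.1):

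1. Add the requirement that no leukemic blasts are present in the peripheral blood on the CBC differential taken with the response marrow. Section 4.6 lets each test move by 3 days, so the text should say which differential is paired with which marrow.
2. State that an assessment meeting PD is not itself scored as CR or CRi. Word this per assessment, so that a response validly documented earlier is not removed by later progression or relapse.
3. State the reference point for the 25% rise in the PD definition.

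The cost is a few lines of text. Table 3 already schedules a CBC with differential on Day 28 of every cycle, so no new test is needed. The reported rate may be slightly lower.

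Separately, the sponsor should reconcile the response categories that lead to consolidation (4.2), the criteria for later cycles (4.4), the progression stopping item (4.11 item 12) and the definitions in 5.1. Whether CRh and MLFS should carry the same blood requirement affects who is eligible for consolidation. That choice, and which clinical rule governs treatment, is for the sponsor to decide.

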5.2. Disease Status Monitoring

Disease status will be confirmed by a bone marrow biopsy within 14 days of study enrollment. Additional bone marrow biopsies will be performed at the end of all cycles of treatment, and at 6 and 12 months post-transplant per the standard-of-care for all patients. MRD status will be assessed concurrently with all bone marrow biopsies via peripheral blood and bone marrow samples. If a bone marrow aspirate cannot be obtained, then MFC should be sent by peripheral blood for MRD monitoring.

6. Pharmaceutical Information

6.1. Flotetuzumab

1. Other Names: MGD006, S80880

2. Classification: Dual-affinity Re-targeting (DART) molecule

3. Mechanism of Action: The dual-affinity re-targeting (DART) molecule flotetuzumab has been shown to increase the interaction between CD123-expressing leukemia cells and T cells by 17-fold *in vitro*.⁵⁶ This interaction has been shown to selectively promote CD4 and CD8 T-cell proliferation in a dose dependent manner, while also activating both CD4 and CD8 T-cells as evidenced by increased CD25 expression. Furthermore, this interaction leads to cellular cytotoxicity in primary AML blasts *in vitro* in the absence and presence of stroma. Subsequently, flotetuzumab was shown to be effective in a murine AML model with a 1415-fold increase in photon flux from leukemic cells in untreated mice as opposed to those treated with flotetuzumab, while a control DART had no effect on tumor growth.⁵⁶

4. Pharmacokinetics: The distribution and clearance of flotetuzumab has been investigated extensively in cynomolgus macaques. The cynomolgus macaque is a reasonable model for humans, as the tissue distribution of CD3 and CD123 is comparable between the two species. The distribution half-life of flotetuzumab is short (~4 minutes) with a volume of distribution of ~1-2 L/kg), which suggests rapid and extensive binding to target cells in tissues. Flotetuzumab was rapidly cleared at the end of infusion with a mean residence time of 7-9 hours, as expected for a molecule of its size (59 kD) that is likely renally cleared.⁵⁷

5. Pharmacodynamics: As CD123 is also highly expressed on plasmacytoid dendritic cells, monocytes, and basophils in addition to leukemic stem cells, it is possible to measure levels of these cell types as a pharmacodynamics marker.⁵⁶ In the cynomolgus macaque, a dose of 100 ng/kg per day led to rapid and extensive depletion of CD123-positive cells with subsequent recovery following treatment discontinuation.⁵⁷

6. Drug Supply: Flotetuzumab drug product (DP) is provided as a sterile aqueous solution with a protein concentration of 0.1 mg/mL in a buffer composed of 10 mM sodium phosphate at pH 6.0, 150 mM sodium chloride and 0.1 mg/mL polysorbate 80. The concentration and function of each component in the DP are summarized below.

Name of Ingredient	Concentration (mg/mL)	Nominal Amount per Vial (mg) ^a	Function
MGD006 drug substance (DS)	0.1	0.5	Active ingredient
Sodium phosphate monobasic monohydrate	1.13	5.65	Buffer component
Sodium phosphate dibasic	0.26	1.3	Buffer component
Sodium Chloride	8.78	43.9	Tonicifier
Polysorbate 80	0.1	0.5	Surfactant

Drug product is supplied as a sterile aqueous solution packaged in a USP and Ph. Eur. conforming Type I borosilicate, 5 cc clear glass vial with a 20 mm 4432/50 gray butyl rubber serum stopper. The vial is sealed with a 20 mm TruEdge aluminum closure with a plastic overseal.

7. MGV002 IV Solution Stabilizer: When administered by a single ambulatory pump or infusion pump configuration, flotetuzumab must be diluted into 0.9% Sodium Chloride Injection, USP (normal saline), containing custom MGV002 Flotetuzumab IV Solution Stabilizer.

The MGV002 Flotetuzumab IV Solution Stabilizer is supplied as a sterile, colorless solution of 0.9% sodium chloride solution with 0.1 mg/mL polysorbate 80. The MGV002 Flotetuzumab IV Solution Stabilizer is packaged in a USP and Ph. Eur. conforming Type I borosilicate, 50 cc clear glass vial with a 20 mm 4432/50 gray butyl rubber serum stopper and sealed with a 20 mm TruEdge aluminum closure with a plastic overseal.

8. Drug Dose Solution Preparation and Administration: Flotetuzumab DP and MGV002 Flotetuzumab IV Solution Stabilizer will be supplied by MacroGenics for use in this study as appropriate to accommodate the method of study drug administration.

Recommended safety measures for handling and preparation include masks, protective clothing, gloves, and vertical laminar airflow safety cabinet.

Flotetuzumab is administered to patients at exceedingly low doses.

All doses employed in this study are described in units of ng/kg/day. Nanogram measurement is infrequently used in clinical practice.

[A nanogram (ng) is
1 billionth (1/10⁹) of a gram (g),
1 millionth (1/10⁶) of a milligram (mg);
and 1 thousandth (1/10³) of a microgram (mg)]

Errors in dilution could result in fatal Cytokine Release Syndrome (CRS).

Every reasonable precaution should be exercised in the preparation, verification, and administration of the Flotetuzumab dose.

Independent verification of patient weight and of the calculated dose must be carried out and documented by a second individual.

Similarly, the administration pump settings should be independently reviewed and documented by a second individual before study drug administration commences.

The method of drug administration is using a single ambulatory pump or infusion pump with flotetuzumab dose solution prepared with 0.9% Sodium Chloride Injection, USP (normal saline) and MGV002 IV Solution Stabilizer, which allows for intravenous infusion up to 7 days before an intravenous bag change is required based on treatment plan.

9. IV Bag for single ambulatory pump infusion: The flotetuzumab dose solution is prepared for administration using either 150 mL or 250 mL empty intravenous bag composed of either polyolefin or PVC.

The method of drug administration is using a single ambulatory pump or infusion pump with flotetuzumab dose solution prepared with MGV002 IV Solution Stabilizer and normal saline which allows for intravenous infusion up to 7 days before an intravenous bag change is required based on treatment plan.

Before administration, the parenteral investigational medicinal products should be visually inspected. Drug should not be administered if discoloration or foreign particulates are observed in the solution.

Prior to adding 0.9% Sodium Chloride Injection, USP (normal saline), MGV002 IV Solution Stabilizer, and flotetuzumab IMP to an empty IV bag as described below for dose preparation, the volume of normal saline needs to be calculated based on the predefined total target volume, the specified MGV002 IV Solution Stabilizer volume, and the flotetuzumab IMP volume calculated from the *Dose Calculation Worksheet*.

- The dose solution preparation begins with the addition of calculated volume of normal saline to an empty IV bag, followed by the addition of a predefined volume of MGV002 IV Solution Stabilizer calculated using the *Dose Calculation Worksheet*.
Normal Saline and MGV002 IV Solution Stabilizer must be added to the IV bag prior to adding flotetuzumab to prevent adsorption of flotetuzumab to the IV bag and administration set.
- Add calculated amount of flotetuzumab IMP into the IV bag containing both normal saline and MGV002 IV Solution Stabilizer. The amount of flotetuzumab IMP calculated for dilution is based upon the patient's weight and the assigned dosing cohort using the *Dose Calculation Worksheet* and the description in the pharmacy manual.
- When diluted during dose preparation, final flotetuzumab concentrations must be within concentration range of **50 ng/mL and 4,167 ng/mL** (concentration will vary per patient's weight) to enable 24 hours or up to 168 hours of IV infusion of doses in the range of 30 ng/kg/day up to 500 ng/kg/day.

Upon completing the dose preparation steps, gently invert the prepared IV bag to mix the dose solution. **THE BAG MUST NOT BE SHAKEN**. Each intravenous bag contains dose-formulated flotetuzumab that is intended to be used for no more than 7-days of intravenous infusion. Flotetuzumab is stable for 192 hours after dilution in MGV002-stabilized normal saline. The dose-formulated flotetuzumab is stable for up to 24 hours of storage after preparation prior to 7-days of administration. During the time of the infusion, the infusion bag and extension set can be exposed to room temperature. However, if administration does not immediately begin, the bag should be stored refrigerated at 2-8°C (36-46°F) until administration can begin, with the time of administration adjusted to account for the maximum of 192 hours of dose-formulated flotetuzumab stability. DO NOT FREEZE the prepared dose solution.

